# Title:

Machine Learning for Postoperative Care

Short Title ODIN-Pilot

Registration: NCT04877535

Version: 3.0; Dec 28 2022

Version 1.10 adds an education and implementation phase between the pre-intervention and post-intervention phases. This will be necessary to give all the participating nurses time to learn where the machine-learning information is located in the Epic environment.

Version 1.11 Clarifies the activities of the education and implementation phase, including the lack of additional consent for notification of the intervention.

Version 2.0 is a major change.

- Parent study (TECTONICS) is closing, remove status as a sub-study.
  - Specify anesthesia-control-tower clinical protocols and equipment instead of TECTONICS protocol
  - b. Remove TECTONICS SMB and DSMB
  - c. Remove TECTONICS data retention
- Remove "short report card" comparator
- Change to inclusion criteria:
  - a. remove "observation unit status" and replace it with "risk of unplanned ICU admission in 85%ile
  - b. add Transplant surgery, Otolaryngology, hepatobiliary surgery to included surgical services
  - c. Remove TECTONICS contact-arm inclusion criterion
  - d. Remove PACU anesthesiologist
  - e. Add previously implicit inclusion criteria: weekdays during business hours
- Modify design from pre- vs post-intervention to pre-intervention plus contemporaneous controls with intervention/no-intervention on alternating days
- Clarify many aspects of intervention screening and mechanics as these have updated
- Rename "run-in phase" to "education and adaptation phase"
- Remove investigator [name] (leaving institution)
- Eliminate secondary outcome measure (handoff checklist)

These changes are based on (1) feedback from existing participants (2) technical issues and time-of-day making the existing recruitment strategy too slow (3) transition of parent RCT to usual clinical operations

# **Version 3**

- Adds additional time because of updates to the format of the report card in response to participant feedback.
- Adds anesthesia clinicians to those who are alerted to the report card
- Adds vascular surgery patients, because the underlying clinical alarms suggest that they are a very relevant group

# Funding:

National Center for Advancing Translational Sciences of the National Institutes of Health under Award Number KL2 TR002346

# **Non-Technical Summary**

Although surgery and anesthesia have become much safer on average, many patients still experience complications after surgery. Some of these complications are likely to be avoided or less severe with early detection and treatment. Barnes-Jewish Hospital has recently started using an Anesthesia Control Tower (ACT), which is a remote group lead by an anesthesiologist who reviews live data from BJH operating rooms and calls the anesthesia provider with concerns to improve reaction times and improve use of best-practices treatments. The ACT also uses machine learning (ML) to calculate patient risks during surgery as a way of measuring when the patient is doing better or worse.

We think that many times the right interpretation of the data or the right treatment to give isn't clear until the surgery is nearly finished. The medical team in the recovery room (post-anesthesia care unit, PACU) and surgical wards is responsible for deciding the treatment strategy, but they don't have all the information available from the intraoperative monitors and events. The patient may still be too sedated or confused from the anesthesia to explain much about their preoperative history. Our goal is to use ML to create a report card for each patient that summarizes the preoperative assessment and intraoperative data in a way that is useful for postoperative providers. In addition to communicating specific facts and risks, the report card may cause the postoperative provider to ask different questions at handoff and spend more time with vulnerable patients.

The goal of this study is to integrate these ML reports into the clinical workflow and to determine if it does affect handoff behavior. The screened patients will be all adults having surgery at BJH with the division of Acute and Critical Care Surgery, Otolaryngology, Hepato-biliary Surgery, and Abdominal Transplant Surgery with elevated risk of unplanned ICU admission. Exclusion criteria are a planned ICU admission or outpatient surgery (no hospital admission).

For each included patient, the ACT clinician will review the report card information, and the postoperative providers will receive it via a print-out or an Epic Best Practices Advisory integrated into their workflow. Our study will include 3 phases: (1) pre-intervention observation of handoff practices, (2) education and workflow adaptation of the intervention, and (3) non-randomized evaluation. During the education and non-randomized evaluation phases, some days will be without-intervention and others with-intervention. On with-intervention days, all eligible patients on a given day will receive the intervention. On without-intervention days no patients will receive the intervention, but handoff outcome measures will be assessed. The main comparison will be between with-intervention and without-intervention days in the evaluation phase. The primary outcome measure we will study is handoff effectiveness in the recovery room or wards. We will also survey providers on any inaccurate items, or major omissions.

This study will be conducted with a waiver of informed consent. It offers non-significant risk to patients. The ML report card will not recommend specific treatments, and decisions will remain in the hands of the supervising physician in all phases of care. The postoperative provider will also be given information about the report card and its limitations.

### 1 Background and Rationale

The operating room (OR) to post-anesthesia care unit (PACU) handoff is a challenging transition for patients where communication errors frequently occur (Segall et al., 2012); subsequent adverse events are common and contribute substantially to mortality, costs, and other patient harms (Hines et al., 1992; Pearse et al., 2006; Story et al., 2010). Preventing loss of information during handoff is an important need to allow accurate early intervention in newly admitted patients. Handoff research has almost exclusively focused on checklists of expertspecified topics that should be discussed. These checklists by their nature do not adapt to the specific patient, and there is a tradeoff between checklist length-thoroughness and user fatiguecompliance. Machine learning risk prediction has been widely recognized for its potential to decrease medical errors and failure to rescue (Xiao et al., 2018). However, provider uptake has been slow, often preferring simple scoring systems (Sanchez-Pinto et al., 2018). Providers skepticism of black box predictions and the difficulty of interpreting ML outputs has been suggested to be a major hindrance (Maddox et al., 2018). As a result, no published research explores the ability of ML to augment information transfer during handoff. Additionally, few clinical ML projects have been rigorously evaluated for changes in user behavior or designed for end-user comprehension; development has focused on raw predictive accuracy, despite many attempts at creating "interpretable" ML. Innovations in ML reports that improve the adoption and provider-understanding of ML predictions are a scalable, low-cost intervention to address the need for improved information transfer and identification of at-risk patients in the postoperative settina.

At BJH, ML-assisted telemedicine for intraoperative providers is provided by the Anesthesia Control Tower (ACT) to allow early identification of errors, optimize early treatments, and prevent lapses in standard of care. The ACT includes ML-based predictions of multiple postoperative complications to identify at-risk and deteriorating patients; the intraoperative provider has indirect access to these predictions via a clinician in the ACT who filters the raw output and considers the ML prediction in their clinical context.

However, the core ACT clinical protocol does not contemplate providing the data summary and ML-prediction information to the receiving provider in the PACU or surgical wards. The proposed Outcome predictions, Data summaries, and Interpretive Notes Report (ODIN-Pilot) study will provide a "report card" containing automatically generated summaries of pre- and intraoperative data along with ML output. This information will be presented to multiple postoperative providers with different contexts and use cases. PACU physicians and registered nurses (RNs) receive handoff from the intraoperative team and assume care for the patient in the immediate postoperative phase (typically 45 minutes to several hours). They observe for appropriate recovery from anesthesia, surveil for developing complications, treat common side effects of anesthesia. When the patient is ready to leave the PACU and communicate their findings to the wards (surgical inpatient unit) RN. The PACU team also communicates to the intraoperative surgical team, who communicates to the wards "midlevel" (advanced practice nurse or resident MD) responsible for routine medical oversight, modifying medication strategies, and ordering additional diagnostic studies if necessary.

We hypothesize several mechanisms by which this ML report card may improve patient outcomes. First, the report card will function as an "alert" for patients at high risk and direct attention to them. This additional review may reduce postoperative complications. Second, the report card may frame handoff communications around important data and issues relevant to the patient. By focusing the postoperative provider on potential problems, it may improve anticipatory guidance between the intraoperative, supervisory, and frontline team members.

This pilot study will not focus on patient outcomes, but will attempt to measure these potential mechanisms. We will survey postoperative providers to measure perceived handoff quality and coverage of important topics. We will validate these surveys with direct observations, debriefing interviews, and structured handoff evaluation tools.

The second objective of this study is to improve the usability of the ML report card and determine the rate at which clinicians believe the information it contains to be inaccurate. Clinical data is often "messy," and it is possible that the mechanisms we use to filter data may make mistakes. We will survey providers on errors (including omissions) to determine the "safety" of our implementation of the postoperative ML report card.

### **1.1 Choice of Comparators**

Based on the lack of existing objective evidence of benefit for ML predictions in the perioperative setting, and the widespread belief that clinicians do not trust ML predictions, we will compare the ML report card intervention to usual care.

## 2 Objectives

The objectives of the study are to determine the interpretability, workflow role, and effect on communications of showing report cards containing ML-based risk profiles based on pre- and intra-operative data to postoperative providers.

### 2.1 Primary Objective

The primary objective will be to determine the effect of postoperative ML report cards on handoff effectiveness.

### 2.2 Secondary Objectives

# 2.2.1 Key Secondary Objectives

The secondary objective is to determine the rate of clinician-noted inaccuracies or major omissions in postoperative ML report cards.

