#### 4.4 Outcomes

# **4.4.1 Primary Outcome Measures**

The primary outcome will be self-reported handoff effectiveness.

The following survey questions will be asked of postoperative providers:

Did you receive at handoff all the information you needed to safely take care of this patient?

[Yes, No]

Did you receive information from the team giving handoff to explicitly help you manage any potential complications or problems? [Yes, No]

If so, please list what problems / topics were discussed? [Free response]

[If with-intervention phase \* ] Did you look at or discuss the postoperative report card for this patient? [Yes, No]

[If  $^*$  yes] Did the report card contain any information that was notably misleading or incorrect?

[Yes, No]

[If yes, please describe: text box]

[If \* yes] Are there any important pieces of information that the computer should have included in the report card but didn't?

[Yes, No]

[If yes, please describe: text box]

[If \* yes] How much did the ML report change questions asked or information transfer at handoff?

[ Not applicable , Not at all , a little , a fair amount , a great amount ]

[If \* yes] How much effort was accessing the report card? [Very easy, easy, some effort, hard, unable to get to it or had to ask for help]

[If \* yes] Was the information presentation in the report card easy to understand? [Easy, some effort, hard to understand, unable to use or had to ask for help]

[If \* yes] Was the information in the report card relevant?
[a great amount, a fair amount, modestly, mostly not, not at all, not sure]

[If \* yes] Was the information in the report card useful to decision making or helpful to your understanding of the patient?
[a great amount, a fair amount, modestly, mostly not, not at all, not sure]

The following questions will additionally be asked of PACU resident physicians:

Did you participate in handoff for this patient? [Yes, No]

Did you visit this patient's bedside or speak to their nurse before being asked to sign them out? [Yes, No]

Figure 7 illustrates the RedCAP survey for safety questions which will be included throughout the study.

Figure 7: RedCAP Safety Survey

Postoperative Al Risk Report Card	Resize font:  Returning?

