### 4.5 Sample Size

Precision on the absolute rate of clinician-rated inaccurate reports depends on the rate, but for 0/150 clinically inaccurate reports, the upper 95% confidence limit is 2.4%. Handoff surveys will be dichotomized into (un)acceptable. If the baseline rate of "acceptable" handoff is 70%, 50 patients without and 100 patients with intervention implies an 18% absolute increase as the minimum change with 80% power. The study is designed primarily to assess the perceived safety and workflow integration of the report card, not any patient outcomes.

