- 5) There are no special circumstances necessitating post-facto information provision to the patient. This requirement is intended for research involving deception.

For direct handoff observations, participants will be approached and provided with study information before handoff begins. We will identify the relevant OR cases and approach the OR staff during emergence from anesthesia. Because the participating PACU and ward nurse is impossible to identify ahead of time (these are assigned throughout the day), we will approach and ask for written consent shortly before handoff begins. We will attempt to approach the pool of PACU nurses with study information during the morning of days on which we plan direct

observations, with the goal of having discussed the study with participants before the patient arrives.

Because many PACU nurse to ward nurse handoffs occur over phone calls, having obtained consent to observed the handoff observation from the PACU nurse, we will disclose our observation of the PACU nurse to any party on the phone, allowing them to request privacy if needed.

No consent will be recorded for the education phase in which we notify staff members how to use the intervention as all information collected in that phase is completely anonymous.

Because of the nature of the intervention. no provisions are made for ancillary post-trial care or participants who are harmed. Participants will receive appropriate care at BJH prior to discharge.

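### One survey question merges seeing the report card with only discussing it, so a provider who could not judge the card can be counted as noting no error

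*Combined protocol and SAP*

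**What the plan says.** Section 2.2.1 states: "The secondary objective is to determine the rate of clinician-noted inaccuracies or major omissions in postoperative ML report cards". Section 1 ties these surveyed errors and omissions to the safety of the implementation.

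The instrument is in 4.4.1. On with-intervention days one Yes/No question opens the report-card items: "Did you look at or discuss the postoperative report card for this patient". A Yes leads to "Did the report card contain any information that was notably misleading or incorrect" and to "Are there any important pieces of information that the computer should have included in the report card but didn't". Each offers Yes or No, with a text box if Yes. The relevance and usefulness items behind the same question offer "a great amount, a fair amount, modestly, mostly not, not at all, not sure".

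Section 4.5 gives the precision: "for 0/150 clinically inaccurate reports, the upper 95% confidence limit is 2.4" per cent. Section 5.3 gives a test for acceptable handoffs and no analysis for the inaccuracy rate.

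The survey can be reached in two ways. Sections 4.3.1 and 4.3.3 put a link and QR code on the print-out and in the Epic advisory. Section 4.4.2 lets a research assistant present the questions after directly observed handoffs, of which there may be up to 150.

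**The concern.** The opening question asks two things at once. Someone who only heard the card mentioned can truthfully answer Yes. That person is then asked whether the card contained wrong or misleading information and whether anything important was missing, with no way to say that they did not see it or could not judge. A No from that person looks the same as a No from someone who read the card and found it sound.

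At stake is the key secondary rate, which the plan uses as evidence of safety. If uninformative No answers are counted, the rate falls and the zero-event limit credits the study with more information than it has. Both errors make the card look safer than the data show.

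**Working it through.** **1. The items side by side (4.4.1).** All sit behind the same opening question.

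| Item | Way out for someone who did not see the card |
|---|---|
| Incorrect or misleading information | None (Yes/No) |
| Important omission | None (Yes/No) |
| Change to handoff | Not applicable |
| Effort of access | Last option merges never reaching the card with needing help |
| Ease of understanding | Last option merges being unable to use it with needing help |
| Relevance, usefulness | Not sure |

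The two items that carry the key secondary rate are the only ones without an exit.

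**2. Who could be a discuss-only respondent.** A provider who opens the survey from the print-out or the Epic advisory has had the card or advisory at hand. The route that does not need the card is the one in 4.4.2, where the assistant may present the questions after an observed handoff. Discussion without sight of the card is possible in this workflow: 7.3 notes "Because many PACU nurse to ward nurse handoffs occur over phone calls", and 4.3.1 says the control tower will not contact PACU nurses or ward providers directly.

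**3. The denominator.** Section 2.2.1 names a rate without a unit, 4.5 counts reports, and 5.3 is silent. Nothing says which ratings count, so nothing excludes discuss-only ratings.

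**4. The plan's own figure.** The exact two-sided 95% upper limit with zero events in n is 1 − 0.025^(1/n). For n = 150 this is 2.43%, which matches the 2.4% in 4.5. The calculation is correct.

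**5. If some of the 150 reports have no informative rating.** Let f be the share of reports rated only by providers who did not see the card. The documents give no value, so f is assumed. The informative number is 150 × (1 − f).

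| f (assumed) | Informative reports | Upper limit, zero events |
|---|---|---|
| 0% | 150 | 2.4% |
| 10% | 135 | 2.7% |
| 20% | 120 | 3.0% |
| 50% | 75 | 4.8% |

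**6. Effect on the rate.** If those reports are counted and all answered No, recorded rate = true rate × (1 − f). A true 5% is recorded as 4.5%, 4.0% or 2.5% at f = 10%, 20% or 50%.

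**7. Why the unit matters.** If the unit is the report and any provider's flag counts, a discuss-only No does harm only where no provider who saw the card rated it. For example, suppose 20% of responses are discuss-only and each report has two independent raters (both assumed). Then f = 0.20 × 0.20 = 4%, n = 150 × 0.96 = 144, and the limit is 1 − 0.025^(1/144) = 2.5%. With one rater per report, f stays at 20% and the limit is 3.0%.

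**The case against.** The case against has several parts.

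- **Main survey route.** The link is on the card or in the advisory, so a ward nurse who only heard about the card by phone does not reach the survey that way. This stands, and it confines the problem largely to assistant-presented surveys. It does not remove it, because 4.4.2 allows that route.
- **Unit.** Section 4.5 counts reports, so extra No answers may change nothing. This stands if reports usually have a rater who saw the card. The plan does not say so.
- **Direction.** A provider who hears the contents at handoff might notice a wrong fact and answer Yes, or might skip the item. This stands: the downward bias is conditional on mostly No answers.
- **Sample size.** Section 4.2.2 plans 350 evaluation patients. At 60 of 90 days that is about 350 × 60/90 = 233 with intervention. With one rating each and 20% removed, about 187 remain, and 1 − 0.025^(1/187) = 2.0%. This is fair, but it needs nearly complete survey response, and the plan gives no response rate.
- **Other safety channels.** The separate REDCap safety form, debriefing interviews and harm reporting (4.4.1, 4.4.2, 6.3) also collect problems. They protect against missing a serious fault, but they do not supply the rate named in 2.2.1.

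A reader might infer that the 2.4% is wrong, that non-viewers certainly enter the denominator, or that phone handoffs make such ratings routine. The documents support none of these: the figure reproduces, no denominator is stated, and the share is unknown. Nor is the problem wholly beyond repair. The access-effort item and the IP-address access log (4.3.3) allow a partial check. It is only partial because reading the paper copy is not logged that way, survey responses carry no identifiers (7.3), and the per-protocol exclusion in 5.3 works by patient, as an exploratory part of the handoff comparison.

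**Conclusion.** The point holds as a defect in the instrument and in the definition of the rate. The survey can record a No on accuracy from a provider who did not see the card, and no stated rule keeps that No out of the key secondary rate.

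The size is conditional. It rests on three assumptions: that some reports are rated only by such providers, that those reports are counted, and that the answers are mostly No. For assumed shares of 10% to 50%, the zero-event limit moves from 2.4% to between 2.7% and 4.8%, and the recorded rate is 90% to 50% of the true rate. If every counted report has a rater who saw the card and could judge it, the 2.4% for 0/150 stands unchanged.

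**What to change.** In 4.4.1, replace the opening question with two: *Did you see the report card (paper or Epic)?* and *Was it discussed at handoff?* Ask the incorrect-information, omission, understanding, relevance and usefulness items only of those who saw the card. Add *could not judge* to the incorrect-information and omission items.

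In 2.2.1 and 4.5, define the rate and the 150 as reports rated by at least one provider who saw the card and could judge it, and state the analysis in 5.3. Report discussion at handoff separately, as a measure of handoff behaviour.

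The cost is one extra survey item, one extra answer option on two items, and a sentence on the denominator. The usable denominator may be slightly smaller, so the limit may be slightly wider.

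For responses already collected on the current form, use the access-effort item and the access log for a sensitivity analysis, and state that it is partial.
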